APPENDIX D. PROTOCOL LABORATORY TESTS

Hematology: Free hemoglobin Haptoglobin Hematocrit Hemoglobin Mean corpuscular hemoglobin Platelet count RBC distribution width RBC mean corpuscular volume RBC count Reticulocyte count White blood cell count White blood cell differential
 
Coagulation Panel: International normalized ratio Prothrombin time Partial thromboplastin time
 
Urine Chemistry: Microalbumin Creatinine Total protein
 
Urinalysis: Albumin Appearance Bilirubin Blood Color Creatinine Glucose Ketone Nitrite pH Protein Specific gravity Urobilinogen
	
Clinical Chemistry: Alanine aminotransferase Albumin Alkaline phosphatase Amylase Aspartate aminotransferase Bicarbonate Blood urea nitrogen C-reactive protein Calcium Chloride Creatinine Gamma-glutamyltransferase Glucose Lactate dehydrogenase Lipase Magnesium Phosphorus Potassium Sodium Total bilirubin (direct and indirect) Total protein Troponin I Uric acid
 
Pregnancy and Menopausal Status Tests: (females only) Beta human chorionic gonadotropin Serum follicle-stimulating hormone (postmenopausal only)
 
Other: ADAMTS13 activity ADA Coombs, direct Free C5 PK Shiga toxin-related HUS screen (eg, Shiga toxin enzyme immunoassay/PCR in stool/stool culture)

--	---

Note: This table excludes exploratory tests

Abbreviations: ADA = antidrug antibodies; ADAMTS13 = a disintegrin and metalloproteinase with a thrombospondin type 1 motif, member 13; APC = alternative pathway of complement; C5 = complement component 5; HUS = hemolytic uremic syndrome; PCR = polymerase chain reaction; PK = pharmacokinetic; RBC = red blood cell

APPENDIX E. EQ-5D-3L

Health Questionnaire

English version for the USA

USA (English) © 1998 EuroQol Group. EQ-5D™ is a trade mark of the EuroQol Group.

By placing a checkmark in one box in each group below, please indicate which statements best describe your own health state today.

Mobility

- I have no problems in walking about
- I have some problems in walking about
- I am confined to bed

Self-Care

- I have no problems with self-care
- I have some problems washing or dressing myself
- I am unable to wash or dress myself

Usual Activities (e.g. work, study, housework, family or leisure activities)

- I have no problems with performing my usual activities
- I have some problems with performing my usual activities
- I am unable to perform my usual activities

Pain / Discomfort

- I have no pain or discomfort
- I have moderate pain or discomfort
- I have extreme pain or discomfort

[figure not shown]
Anxiety / Depression

- I am not anxious or depressed
- I am moderately anxious or depressed
- I am extremely anxious or depressed

To help people say how good or bad a health state is, we have drawn a scale (rather like a thermometer) on which the best state you can imagine is marked 100 and the worst state you can imagine is marked 0.

We would like you to indicate on this scale how good or bad your own health is today, in your opinion. Please do this by drawing a line from the box below to whichever point on the scale indicates how good or bad your health state is today.

Your own health state today

APPENDIX F. FACIT-FATIGUE

FACIT Fatigue Scale (Version 4)

Header to be completed by study site	
Study Number: ALXN1210-aHUS-311	Subject ID: _____
Date Completed: _____	Time Completed: _____

Below is a list of statements that other people with your illness have said are important. Please circle or mark one number per line to indicate your response as it applies to the past 7 days.

		Not at all	A little bit	Some- what	Quite a bit	Very much
HI7	I feel fatigued	0	1	2	3	4
HI12	I feel weak all over	0	1	2	3	4
An1	I feel listless ("washed out")	0	1	2	3	4
An2	I feel tired	0	1	2	3	4
An3	I have trouble starting things because I am tired.....	0	1	2	3	4
An4	I have trouble finishing things because I am tired	0	1	2	3	4
An5	I have energy	0	1	2	3	4
An7	I am able to do my usual activities	0	1	2	3	4
An8	I need to sleep during the day.....	0	1	2	3	4
An12	I am too tired to eat	0	1	2	3	4
An14	I need help doing my usual activities	0	1	2	3	4
An15	I am frustrated by being too tired to do the things I want to do.....	0	1	2	3	4
An16	I have to limit my social activity because I am tired.....	0	1	2	3	4

APPENDIX G. PEDIATRIC FACIT-FATIGUE

Pediatric (Paediatric) Functional Assessment of Chronic Illness Therapy – Fatigue

Header to be completed by study site	
Study Number: ALXN1210-aHUS-311	Subject ID: _____
Date Completed: _____	Time Completed: _____
Completed by:  Patient  Caregiver (Initials): _____	

Below is a list of statements that other people with your illness have said are important. Please circle or mark one number per line to indicate your response as it applies to the past 7 days.

		None of the time	A little bit of the time	Some of the time	Most of the time	All of the time
pF1	I feel tired.....	0	1	2	3	4
pF2	I have energy (or strength).....	0	1	2	3	4
pF3	I could do my usual things at home	0	1	2	3	4
pF4	I had trouble starting things because I was too tired.....	0	1	2	3	4
pF5	I had trouble finishing things because I was too tired	0	1	2	3	4
pF6	I needed to sleep during the day	0	1	2	3	4
pF7	I got upset by being too tired to do things I wanted to do .	0	1	2	3	4
pF8	Being tired made it hard for me to play or go out with my friends as much as I'd like.....	0	1	2	3	4
pF9	I needed help doing my usual things at home.....	0	1	2	3	4
pF10	I feel weak.....	0	1	2	3	4
pF11	I was too tired to eat.....	0	1	2	3	4
pF12	Being tired made me sad.....	0	1	2	3	4
pF13	Being tired made me mad (angry)	0	1	2	3	4

APPENDIX H. RESOURCE UTILIZATION PATIENT QUESTIONNAIRE

Patient Questionnaire

RESOURCE UTILIZATION

1. Have you visited your health care provider for management of complications related to your aHUS within the past month?
 No
 Yes, specify number of health care provider visits in the past month: _____
2. Have you gone to an Emergency Room primarily for treatment of complications related to your aHUS in the past month?
 No
 Yes, specify number of emergency room visits in the past month: _____
3. Have you been admitted to the Hospital primarily for treatment of complications related to your aHUS in the past month?
 No
 Yes, specify number of hospital admissions in the past month: _____
4. Have you missed work or school as a result of complications or symptoms related to your aHUS within the past month?
 No
 Yes, specify number of work days missed in the past month: _____

GENERAL HEALTH

5. In general would you say your health is:
- Excellent Very good Good Fair Poor

WORK STATUS

6. What is your current work status?
- Work full time at a paid job
 Work part time at a paid job (less than 30 hours per week)
 Not in paid work force due to aHUS
 Not working full time due to aHUS
 Not working for pay for reasons unrelated to aHUS
 Student
 Retired
 Other, specify: _____

APPENDIX I. PATIENT-REPORTED aHUS SYMPTOMS QUESTIONNAIRE

PATIENT-REPORTED aHUS SYMPTOMS													
Date Completed: ___ / ___ / ___ 
 dd mm yyyy 
													
During the past week did you have any of the following symptoms?	Symptoms present?	If YES, how often did you have it?				If YES, how severe was it usually?				If YES, how much did it distress or bother you?			
		Rarely	Occasionally	Frequently	Almost constantly	Slight	Moderate	Severe	Very Severe	Not at all	A little bit	Somewhat	Quite a bit
Yellow discoloration of eyes and/or skin (jaundice)	 No  Yes												
Chest pain	 No  Yes												
Shortness of breath	 No  Yes												
Headache	 No  Yes												
Confusion	 No  Yes												
Irritability	 No  Yes												
Anxiety	 No  Yes												
Weakness	 No  Yes												
Fatigue	 No  Yes												
Easy bruising/abdominal bleeding	 No  Yes												
Abdominal pain	 No  Yes												
Nausea/vomiting	 No  Yes												
Diarrhea	 No  Yes												
Swelling	 No  Yes												
Other, specify:	 No  Yes												
Other, specify:	 No  Yes												
Other, specify:	 No  Yes												
Other, specify:	 No  Yes												
Other, specify:	 No  Yes												
Other, specify:	 No  Yes												

APPENDIX J. GLOMERULAR FILTRATION RATE CATEGORY/STAGE IN CHRONIC KIDNEY DISEASE

GFR Category/Stage	GFR (mL/min/1.73 m ²)	Terms
G1	≥ 90	Normal or High
G2	60 - 89	Mildly Decreased ^a
G3a	45 - 59	Mildly to Moderately Decreased
G3b	30 - 44	Moderately to Severely Decreased
G4	15 - 29	Severely Decreased
G5	< 15	Kidney Failure

^a Relative to young adult level

Note: In the absence of evidence of kidney damage, neither GFR category/stage G1 nor G2 fulfill the criteria for CKD

Source: [KDIGO 2012 Clinical Practice Guideline for the Evaluation and Management of Chronic Kidney Disease. 2013. 3: 19-62.](#)

3. LIST OF ABBREVIATIONS AND DEFINITIONS OF TERMS

The following abbreviations and acronyms are used in this Statistical Analysis plan (SAP).

Table 1: Abbreviations and Acronyms

Abbreviation or acronym	Explanation
ADA	Antidrug antibodies
ADAMTS13	A disintegrin and metalloproteinase with a thrombospondin type 1 motif, member 13
ADL	Activities of daily living
AEs	Adverse events
aHUS	Atypical hemolytic uremic syndrome
BP	Blood pressure
C5	Complement component 5
CDF	Cumulative distribution function
CI	Confidence interval
CKD	Chronic kidney disease
CSR	Clinical Study Report
CTCAE	Common Terminology Criteria for Adverse Events
ECG	Electrocardiogram
eCRF	Electronic Case Report Form
eGFR	Estimated Glomerular Filtration Rate
EQ-5D-3L	EuroQol 5 dimensions 3 level
FACIT	Functional assessment of chronic illness therapy
FAS	Full Analysis Set
IV	Intravenous
LDH	Lactate dehydrogenase
LLT	Lowest level term
LOCF	Last Observation Carried Forward
MedDRA	Medical Dictionary for Regulatory Activities
mITT	Modified intent to treat
MMRM	Mixed model for repeated measures
PD	Pharmacodynamic
PE/PI	Plasma exchange/plasma infusion
PK	Pharmacokinetic
PT	Preferred Term (MedDRA)
PTAEs	PreTreatment Adverse Events
QoL	Quality of life
q8w	Once every 8 weeks
SAEs	Serious adverse events
SAS [®]	Statistical Analysis Software [®]
SAP	Statistical Analysis Plan
SD	Standard deviation
SOC	System Organ Class (MedDRA)
SOP	Standard operating procedure
TEAEs	Treatment-Emergent Adverse Events
TMA	Thrombotic microangiopathy

[figure not shown]
4. DESCRIPTION OF THE PROTOCOL

ALXN1210-aHUS-311 is a Phase 3, single arm, multicenter study to evaluate the safety and efficacy of ALXN1210 administered by intravenous (IV) infusion to adolescent (12 to < 18 years of age) and adult (≥ 18 years of age) patients with atypical hemolytic uremic syndrome (aHUS). All patients must be naïve to complement inhibitor treatment; at least 6 and up to 10 adolescent (12 to < 18 years of age at Screening) patients and at least 10 and up to 25 patients with prior kidney transplants will be included.

The study consists of an up to 7 day Screening Period, a 26-week Initial Evaluation Period, and an Extension Period of up to 2 years. Dosages are based on the patient’s last recorded study visit body weight. Patients will receive a loading dose of ALXN1210 IV (2400 mg for patients weighing ≥ 40 to < 60 kg, 2700 mg for patients weighing ≥ 60 to < 100 kg, 3000 mg for patients weighing ≥ 100 kg) on Day 1, followed by maintenance doses of ALXN1210 IV (3000 mg for patients weighing ≥ 40 to < 60 kg, 3300 mg for patients weighing ≥ 60 to < 100 kg, 3600 mg for patients weighing ≥ 100 kg) on Day 15 and once every 8 weeks (q8w) thereafter for a total of 26 weeks of treatment. After the Initial Evaluation Period, patients will enter an Extension Period and receive ALXN1210 until the product is registered or approved (in accordance with country specific regulations) or for up to 2 years, whichever occurs first. The end of trial is defined as the last patient’s last visit.

Figure 1: Study Design Schematic for Clinical Protocol ALXN1210-aHUS-311 illustrates the study design.

Figure 1: Study Design Schematic for Clinical Protocol ALXN1210-aHUS-311

The primary objective of the study is to assess the efficacy of ALXN1210 in patients with aHUS to inhibit complement-mediated thrombotic microangiopathy (TMA) as characterized by thrombocytopenia, hemolysis, and renal impairment, as determined by Complete TMA Response following treatment.

Secondary objectives of the study include the following:

1. To characterize the safety and tolerability of ALXN1210 in this patient population
2. To evaluate the efficacy of ALXN1210 by the following additional measures:

- a. Dialysis requirement status
 - b. Time to Complete TMA Response
 - c. Complete TMA Response status over time
 - d. Observed value and change from baseline in estimated glomerular filtration rate (eGFR)
 - e. Chronic kidney disease (CKD) stage, as evaluated by eGFR at select target days and classified as improved, stable (no change), or worsened compared to baseline
 - f. Observed value and change from baseline in hematologic parameters (platelets, lactate dehydrogenase (LDH), hemoglobin)
 - g. Increase in hemoglobin of ≥ 20 g/L from baseline, observed at two separate assessments obtained at least 4 weeks (28 days) apart, and any measurement in between
 - h. Change from baseline in quality of life (QoL), as measured by EuroQol 5 dimensions 3 level (EQ-5D-3L; all patients), Functional Assessment of Chronic Illness Therapy (FACIT) Fatigue version 4 (patients ≥ 18 years of age), and Pediatric FACIT Fatigue (patients < 18 years of age) questionnaires
3. To characterize the pharmacokinetic (PK)/pharmacodynamics (PD) of ALXN1210 by the following measures:
 - a. Changes in serum ALXN1210 concentration over time
 - b. Changes in free complement component 5 (C5) concentrations over time
 4. To evaluate the long term safety and efficacy of ALXN1210

For additional details, refer to the protocol.

4.1. Changes from Analyses Specified in the Protocol

None

4.2. Changes from Analyses Specified in the Previous Version of the SAP

The original SAP (dated 30 January 2017) was amended 3 times. A summary of the changes is presented below.

4.2.1. SAP version 2 (dated 24 March 2017)

- In [Section 9.4.7](#), applied changes to the list of preferred terms to search for adverse events related to meningococcal infection. The following preferred terms were removed: Neisseria infection, Septic arthritis neisserial, and Neisseria test positive.
- In [Section 5.2.1](#), added footnotes to [Table 2](#).
- In [Section 6.2](#), deleted the requirement for satisfaction of exclusion criteria 1 and 2 for inclusion in the per protocol set. This was a redundant condition because these criteria need to be satisfied to be included in the full analysis set.
- In [Section 7.1.2](#), fixed an omission error by adding exclusion criterion 2 to the 5th item on the list for consistency.

- In [Section 7.1.2](#), removed the specification for production of a table presenting the number and percentage of patients meeting or not meeting inclusion/exclusion criteria. A listing is deemed sufficient.
- In [Section 7.2.1.1](#), removed the statement “If a Day 1 pretreatment assessment is missing, the Screening assessment will be used as the baseline assessment” which is superfluous given that the baseline value is based on the average of the Screening and Day 1 assessments.
- In [Section 7.2.2.8](#), the description for a new table was added. The number and proportion of patients with a 3 point improvement from baseline in the FACIT Fatigue score will be summarized over time by presenting the number and proportion of patients along with a 2-sided 95% CI for each postbaseline time point.

4.2.2. SAP version 3 (dated 15 September 2017)

- In [Section 5.2.3](#), added text explaining that evaluation of Inclusion Criteria 2a and 2b may be based on local laboratory results within 28 days prior to the start of the Screening Period or laboratory results obtained during the Screening Period from a local or central laboratory.
- In [Section 6.1](#), adjusted the first bullet in the list of criteria to be met for inclusion in the full analysis set to reflect the change in Protocol Amendment 3, dated 19 July 2017.
- In [Section 6.2](#), added inclusion criterion 2 and exclusion criterion 7 to the list of criteria to be satisfied for inclusion in the per protocol set.
- In [Section 7.1.2](#), item 5 was adjusted to reflect that violation of inclusion criterion 2c should result in study discontinuation to reflect the change in Protocol Amendment 3, dated 19 July 2017. Item 6 was deleted as there is no randomization and enrollment quotas will be verified.
- In [Section 7.2.1.2](#), added a subgroup for patients that met all laboratory criteria for TMA as determined by the central laboratory at Day 1.

4.2.3. Current SAP (version 4)

- In [Section 5.2.3](#), added text specifying that local laboratory results may be used for analysis when no central laboratory results are available. Text was also added to this section to address in vitro erythrocyte lysis referred to as table top hemolysis (TTH) caused by sample mishandling.
- In [Section 7.2.2.3](#) an example indicating patients to be included in a summary of response by visit was deleted as it was incorrectly implying that certain patients would be excluded from some time points.
- In [Section 9.4.10](#), added text indicating that the exclusion from analysis of hemoglobin and platelets results when concurrent with blood transfusion is only

applicable to postbaseline assessments. Because pre-treatment assessments, even if concurrent with blood transfusion, need to meet the inclusion criteria.

4.3. Planned Analyses

An interim analysis is planned for this study at the end of the 26-week Initial Evaluation Period after all patients have completed or withdrawn from the 26-week Initial Evaluation Period. This analysis will allow for evaluation of the primary endpoint and will be the basis for the initial clinical study report (CSR).

The final analysis which will summarize long-term efficacy, safety, and PK parameters will be performed at the end of the 2-year Extension Period.

The present document serves to describe both of these planned analyses.

5. DEFINITIONS

5.1. Efficacy

5.1.1. Primary Endpoint(s)

The primary efficacy endpoint of the study is Complete TMA Response during the 26 week Initial Evaluation Period. The criteria for Complete TMA Response are the following:

1. Normalization of platelet count (defined as platelet count $\geq 150,000$ per microliter)
2. Normalization of LDH (defined as LDH \leq upper limit of normal)
3. $\geq 25\%$ improvement in serum creatinine from baseline

Patients must meet all Complete TMA Response criteria at 2 separate assessments obtained at least 4 weeks (28 days) apart, and any measurement in between.

5.1.2. Secondary Endpoints

The secondary efficacy endpoints of the study are the following:

1. Dialysis requirement status
2. Time to Complete TMA Response
3. Complete TMA Response status over time
4. Observed value and change from baseline in eGFR
5. CKD stage, as evaluated by eGFR at select target days and classified as improved, stable (no change), or worsened compared to baseline
6. Observed value and change from baseline in hematologic parameters (platelets, LDH, hemoglobin)
7. Increase in hemoglobin of ≥ 20 g/L from baseline, observed at 2 separate assessments obtained at least 4 weeks (28 days) apart, and any measurement in between
8. Change from baseline in QoL, as measured by EQ-5D-3L (all patients), FACIT Fatigue version 4 (patients ≥ 18 years of age), and Pediatric FACIT Fatigue (patients < 18 years of age) questionnaires

5.1.3. Exploratory Endpoints

Patients will report signs or symptoms of aHUS and resource utilization using the Patient-reported aHUS Symptoms Questionnaire and the Resource Utilization Patient Questionnaire, respectively.

The Investigator will evaluate extra-renal signs or symptoms of aHUS using a composite of clinical laboratory measurements, vital signs, and an organ system review.

5.1.4. Other Efficacy Endpoints

Not applicable

5.2. Safety

The safety and tolerability of ALXN1210 will be evaluated by physical examinations, vital signs, electrocardiograms (ECGs), laboratory assessments, and incidence of adverse events (AEs) and serious adverse events (SAEs). The proportion of patients who develop antidrug antibodies (ADA) will also be assessed.

5.2.1. Adverse Events

Treatment-emergent AEs (TEAEs) are defined as any event not present prior to exposure to Investigational Product or any event already present that worsens in either intensity or frequency following exposure to Investigational Product. An AE will be considered a TEAE if the start date and time is on or after the start date and time of the first study drug infusion. All other AEs are considered PreTreatment Adverse Events (PTAEs).

The severity of AEs will be graded using Common Terminology Criteria for Adverse Events (CTCAE) version 4.03 or higher. A grading (severity) scale is provided for each AE term. Each LLT will be coded to a MedDRA preferred term.

Grade refers to the severity of the AE. The CTCAE assigns a grade of 1 through 5, with unique clinical descriptions of severity for each AE (Table 2).

Table 2: Adverse Event Severity Grading Scale

Grade	Description
Grade 1	Mild; asymptomatic or mild symptoms; clinical or diagnostic observations only; intervention not indicated
Grade 2	Moderate; minimal, local or noninvasive intervention indicated; limiting age-appropriate instrumental activities of daily living (ADL) ^a
Grade 3	Severe or medically significant, but not immediately life-threatening; hospitalization or prolongation of hospitalization indicated; disabling; limiting self-care ADL ^b
Grade 4	Life-threatening consequences; urgent intervention indicated.
Grade 5	Death related to AE.

Abbreviations: ADL = activities of daily living; AE = adverse event

^a Instrumental ADL refers to preparing meals, shopping for groceries or clothes, using the telephone, managing money, etc.

^b Self-care ADL refers to bathing, dressing and undressing, feeding self, using the toilet, taking medications, and not bedridden.

An Investigator must provide a causality assessment (Unrelated, Unlikely, Possible, Probable, or Definite) for all AEs (both serious and nonserious) based upon the Investigator's medical judgment and the observed symptoms associated with the event (Table 3).

Table 3: Causality Assessment Descriptions

Assessment	Description
Not Related/Unrelated	Suggests that there is no causal association between the investigational product and the reported event.

Assessment	Description
Unlikely Related	Suggests that the clinical picture is highly consistent with a cause other than the investigational product but attribution cannot be made with absolute certainty and a relationship between the investigational product and AE cannot be excluded with complete confidence.
Possibly Related	Suggests that treatment with the investigational product may have caused or contributed to the AE (ie, the event follows a reasonable temporal sequence from the time of drug administration and/or follows a known response pattern to the investigational product, but could also have been produced by other factors).
Probably Related	Suggests that a reasonable temporal sequence of the event with the investigational product administration exists and the likely causal association of the event with the investigational product. This will be based upon the known pharmacological action of the investigational product, known or previously reported adverse reactions to the investigational product or class of drugs, or judgment based on the Investigator's clinical experience.
Definitely Related	Temporal relationship to the investigational product, other conditions (concurrent illness, concurrent medication reaction, or progression/expression of disease state) do not appear to explain event, corresponds with the known pharmaceutical profile, improvement on discontinuation, reappearance on rechallenge.

For more details see Section 11.7 of the protocol, and [Section 9.4](#) of this SAP.

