11.7.2. Severity Assessment

The severity of AEs will be graded using Common Terminology Criteria for Adverse Events (CTCAE) version 4.03 or higher. A grading (severity) scale is provided for each AE term. Each CTCAE term is a Lowest Level Term (LLT) per the Medical Dictionary for Regulatory Activities (MedDRA[®]). Each LLT will be coded to a MedDRA preferred term (PT).

Grade refers to the severity of the AE. The CTCAE assigns a grade of 1 through 5, with unique clinical descriptions of severity for each AE ([Table 7](#)).

Table 7: Adverse Event Severity Grading Scale

Grade	Description
Grade 1	Mild; asymptomatic or mild symptoms; clinical or diagnostic observations only; intervention not indicated
Grade 2	Moderate; minimal, local or noninvasive intervention indicated; limiting age-appropriate instrumental activities of daily living (ADL) ^a
Grade 3	Severe or medically significant, but not immediately life-threatening; hospitalization or prolongation of hospitalization indicated; disabling; limiting self-care ADL ^b
Grade 4	Life-threatening consequences; urgent intervention indicated.
Grade 5	Death related to AE.

Abbreviations: ADL = activities of daily living; AE = adverse event

^a Instrumental ADL refers to preparing meals, shopping for groceries or clothes, using the telephone, managing money, etc.

^b Self-care ADL refers to bathing, dressing and undressing, feeding self, using the toilet, taking medications, and not bedridden.

Any change in the severity of an AE should be documented based on specific guidelines in the eCRF Completion Guidelines.

Severity and seriousness must be differentiated: severity describes the intensity of an AE, while the term seriousness refers to an AE that has met specific criteria for a SAE as described in [Section 11.7.4](#).

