15.9.1. Adverse Events

The following definitions will be used for AEs:

- Pretreatment adverse events: Any AE that starts after providing informed consent, but before the first infusion of study drug
- Treatment-emergent adverse event: Any AE that starts during or after the first infusion of study drug. Adverse events that start 56 days or later after the last dose of study drug will not be considered as treatment emergent.
- Treatment-emergent SAE: A treatment-emergent AE (TEAE) that is serious ([Section 11.7.4](#) for definitions).

The incidence of TEAEs, TEAEs leading to withdrawal from the study, TEAEs leading to study treatment discontinuation, drug-related TEAEs, TEAEs during study drug administration, severe TEAEs, and SAEs will be summarized. All AEs will be coded using MedDRA version 18 or higher, and will be summarized by system organ class (SOC) and PT overall, by severity, and by relationship to treatment. Detailed by-patient listings of TEAEs, SAEs, related TEAEs, TEAEs during study drug administration, TEAEs leading to withdrawal from the study, and TEAEs leading to study treatment discontinuation will be provided.

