7.3.2. Adverse Events (AEs)

The following definitions will be used for AEs:

- Pretreatment adverse events: Any AE that starts after providing informed consent, but before the first infusion of study drug
- Treatment-emergent adverse event: Any AE that starts during or after the first infusion of study drug.
- Treatment-emergent SAE: A treatment-emergent AE (TEAE) that is serious.

PreTreatment Adverse Events will be summarized in listings and Treatment-Emergent Adverse Events will be tabulated and presented as described below.

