9.4.6. Adverse Events

The analysis of Adverse Events is described in detail in [Section 7.3.2](#).

Treatment-emergent AEs (TEAEs) are events with start dates and start times on or after the date and time of the first study drug dose. If the start date of an AE is partially or completely missing and the end (stop) date and time of the AE does not indicate that it occurred prior to first dose, then the determination of treatment-emergent status will be based on the following:

- If the start year is after the year of the first study drug dose, then the AE is treatment-emergent; else,

- If the start year is the same as the year of the first study drug dose and
 - the start month is missing, then the AE is treatment emergent; else if
 - the start month is present and is the same or after the month of the first study drug dose, then the AE is treatment-emergent; else,
- If the start date is completely missing, then the AE is treatment-emergent.

All other AEs are considered PreTreatment Adverse Events (PTAEs).

Related AEs are defined as possible, probable or definitely related. Unrelated AEs are defined as unlikely or not related.

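### SAP 5.2.1 counts on-drug worsening of an existing event as treatment-emergent, but the start-date rule leaves such an event out of the TEAE tables when it stays on one record with a predose start

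*SAP*

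**What the plan says.** SAP 5.2.1 first counts as treatment-emergent both events that were absent before exposure and "any event already present that worsens in either intensity or frequency following exposure to Investigational Product". Its next sentence is a date test: "An AE will be considered a TEAE if the start date and time is on or after the start date and time" of the first infusion. The sentence after that assigns the remainder: "All other AEs are considered PreTreatment Adverse Events (PTAEs".

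Three other places give the date test alone:

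- SAP 7.3.2: "Any AE that starts during or after the first infusion of study drug".
- SAP 9.4.6, within the technical specifications for derived variables: "Treatment-emergent AEs (TEAEs) are events with start dates and start times on or after the date and time of the first study drug dose".
- Protocol 15.9.1: "Treatment-emergent adverse event: Any AE that starts during or after the first infusion of study drug". The protocol also sets an upper limit of 56 days after the last dose, which does not affect this point.

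SAP 7.3.2 sends pretreatment AEs to listings and TEAEs to tables. The tables by system organ class and preferred term, by relationship and by severity (SAP 7.3.2.2 to 7.3.2.4) count TEAEs. On data capture, protocol 11.7.2 says "Any change in the severity of an AE should be documented", and leaves the method to eCRF Completion Guidelines that are in neither document.

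**The concern.** For an event that begins before the first infusion and worsens after it, the first and third sentences of SAP 5.2.1 give opposite answers. Section 9.4.6 is where a programmer would look, and it holds only the date test, so that is the rule likely to be run.

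The route is open. Protocol 11.7 has AEs recorded from consent, and patients enter with evidence of thrombotic microangiopathy, some needing dialysis for acute kidney injury, so an AE before the first dose is plausible.

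What is at stake is the main safety display. The events at risk of being left out are those that became worse after dosing. The overall summary in SAP 7.3.2.1 also counts fatal events and events leading to discontinuation or withdrawal as TEAEs, so it is gated by the same classification.

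**Working it through.** The plan states no figure on this point, so there is none to reproduce. The check sets the rules side by side and then runs test records through them.

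**1. The two rules.** For records with complete dates:

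- Date rule (SAP 5.2.1 second sentence, 7.3.2, 9.4.6; protocol 15.9.1): TEAE if start ≥ first infusion.
- Definition (SAP 5.2.1 first sentence): TEAE if start ≥ first infusion, or if start < first infusion and the event worsens in intensity or frequency afterwards.

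The first set lies inside the second. The difference is exactly the records with a predose start that worsen on drug. Neither document specifies a grade change, a frequency change or a worsening date from which to derive that group.

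**2. Test records under SAP 9.4.6.** The first infusion is assumed to be 15 June 2017, 10:00, for illustration only.

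| Case | Record | Result |
|---|---|---|
| A | One record, onset 12 June after consent at Grade 1, Grade 3 from 20 June, start date kept | Pretreatment |
| B | Same event split: Grade 1 record from 12 June | Pretreatment |
| B | Same event split: new Grade 3 record from 20 June | TEAE |
| C | Condition in medical history, worsening entered as an AE starting 20 June | TEAE |
| D | Predose onset in the month of first dose, day missing, ongoing | TEAE |
| E | Predose onset in the previous month, day missing | Pretreatment |
| F | Start date wholly missing, ongoing | TEAE |

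The worsening is left out of the tables in case A, and in case E if that event worsens. It is not left out in B, C, D or F. Case E tests the rule only. With Screening of up to 7 days, a first dose on 15 June puts the start of Screening at about 8 June (15 − 7), so a previous-month onset needs a first dose in roughly the first week of a month.

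**3. Size.** The exposed records are mainly AEs starting between consent and first infusion. The documents give no rate for such AEs and none for their worsening. Per patient the scale is 1/55 = 0.018, or 1.8% of planned enrolment. That is a unit of scale, not an estimate.

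**4. Direction.** Because the date-rule set lies inside the definition set (step 1), this mechanism can only lower TEAE counts.

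**The case against.** The strongest reply is that the operative rule is consistent. Protocol 15.9.1, SAP 7.3.2 and SAP 9.4.6 all use start date, and one introductory sentence is the outlier. Start date only, with worsening captured as a new record, is a legitimate convention. This stands as a reason to offer deletion of the clause as an alternative fix. It does not remove the contradiction, because the SAP never says that worsening opens a new record.

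A second reply is that much worsening is captured by other routes. Protocol 11.7 exempts pre-existing conditions from being AEs only if they do not worsen. Protocol 11.4 makes clinically significant laboratory changes from baseline AEs, and protocol 15.9.2 does the same for adverse examination changes. This also stands, and it narrows the exposed set. None of these passages says that an AE already recorded in Screening receives a new start date. Protocol 11.7.2 speaks of severity only, so worsening in frequency has no stated route.

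A reader might infer three stronger things that the documents do not support:

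- *Every worsening event leaves all the tables.* The outcome turns on the unseen eCRF guidelines, and cases B, C, D and F are tabulated. Nothing disappears from the report: SAP 7.3.2.1 lists all AEs with severity and relationship, and SAP 7.3.2.5 lists fatal AEs and those leading to discontinuation or withdrawal. The meningococcal search in SAP 9.4.7 covers the whole AE dataset, with medical review.
- *The serious-event tables lose these events too.* This is possible but not established. Protocol 15.9.1 names SAEs without limiting them to treatment-emergent ones, and the SAP says only that SAEs are summarised in a similar way, while SAP 7.3.2 sends pretreatment events to listings.
- *The safety tables as a whole are biased towards the drug.* The direction in step 4 holds for this mechanism alone. The incomplete-date rules lean the other way: for example, if "the start month is present and is the same or after the month of the first study drug dose, then the AE is treatment-emergent", even where true onset was before the dose.

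**Conclusion.** The contradiction is real and is more than missing detail, since the residual rule in SAP 5.2.1 misclassifies an event by the SAP's own definition. The consequence is conditional. It applies to an AE with onset between consent and first infusion, held as one record with its predose start date, that worsens in intensity or frequency on drug.

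The number of such events is probably small and cannot be computed from the documents. The conclusion assumes that SAP 9.4.6 is programmed as written and that at least some worsening events keep a single record. If the eCRF guidelines require a new record at every worsening, including worsening in frequency, the loss vanishes and only the wording conflict remains. The point should be settled because this definition gates the principal safety tables and the repair is cheap.

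**What to change.** **If worsening is meant to count.** In SAP 7.3.2 and 9.4.6, state that an AE with predose onset whose CTCAE grade or frequency increases after the first infusion is treatment-emergent from the date of worsening, and is tabulated at the postdose grade. Align SAP 5.2.1, including its residual sentence, and protocol 15.9.1 with this. State in the SAP that the eCRF records a worsening, in intensity or frequency, as a new dated record. Without that date the derivation cannot be run.

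**If start date alone is meant.** Delete the worsening clause from SAP 5.2.1, and tabulate separately the pretreatment AEs that worsen after dosing.

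**Cost.** A few sentences and one extra derivation. TEAE counts may rise slightly under the first option. If the eCRF guidelines do not already capture the date of worsening, that capture has to be added.
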